5.3 METHODS AND TIMING FOR CAPTURING AND ASSESSING SAFETY PARAMETERS

The investigator is responsible for ensuring that all adverse events (see Section 5.2.1 for definition) are recorded on the Adverse Event eCRF and reported to the Sponsor in accordance with instructions provided in this section and in Sections 5.4–5.6.

For each adverse event recorded on the Adverse Event eCRF, the investigator will make an assessment of seriousness (see Section 5.2.2 for seriousness criteria), severity (see Section 5.3.3), and causality (see Section 5.3.4).

5.3.1 Adverse Event Reporting Period

Investigators will seek information on adverse events at each patient contact. All adverse events, whether reported by the patient or noted by study personnel, will be recorded in the patient's medical record and on the Adverse Event eCRF.

After informed consent has been obtained but prior to initiation of study drug, only serious adverse events caused by a protocol-mandated intervention (e.g., invasive procedures such as biopsies, discontinuation of medications) should be reported (see Section 5.4.2 for instructions for reporting serious adverse events).

Emicizumab—F. Hoffmann-La Roche Ltd 64/Protocol BO41423, Version 3

After initiation of study drug, all adverse events will be reported until the patient completes his or her last study visit.

Instructions for reporting adverse events that occur after the adverse event reporting period are provided in Section 5.6.

5.3.2 Eliciting Adverse Event Information

A consistent methodology of non-directive questioning should be adopted for eliciting adverse event information at all patient evaluation timepoints. Examples of non-directive questions include the following:

"How have you felt since your last clinic visit?"

"Have you had any new or changed health problems since you were last here?"

5.3.3 Assessment of Severity of Adverse Events

The WHO Toxicity Grading Scale (see Appendix 12) will be used for assessing adverse event severity. Table 2 will be used for assessing severity for adverse events that are not specifically listed in the WHO Toxicity Grading Scale.

Table 2 Adverse Event Severity Grading Scale for Events Not Specifically Listed in WHO Toxicity Grading Scale

Grade	Severity
1	Mild; transient or mild discomfort (<48 hours); no medical intervention or therapy required
2	Moderate; mild to moderate limitation in activity; some assistance may be needed; no or minimal medical intervention or therapy required
3	Severe; marked limitation in activity; some assistance usually required; medical intervention or therapy required; hospitalization possible
4	Life-threatening; extreme limitation in activity; significant assistance required; significant medical intervention or therapy required, hospitalization or hospice care probable

Notes: Developed by the Division of Microbiology and Infectious Diseases.

Regardless of severity, some events may also meet seriousness criteria. Refer to definition of a serious adverse event (see Section 5.2.2).

5.3.4 Assessment of Causality of Adverse Events

Investigators should use their knowledge of the patient, the circumstances surrounding the event, and an evaluation of any potential alternative causes to determine whether an adverse event is considered to be related to the study drug, indicating "yes" or "no" accordingly. The following guidance should be taken into consideration:

- Temporal relationship of event onset to the initiation of study drug
- Course of the event, with special consideration of the effects of dose reduction, discontinuation of study drug, or reintroduction of study drug (as applicable)

Emicizumab—F. Hoffmann-La Roche Ltd 65/Protocol BO41423, Version 3

- Known association of the event with the study drug or with similar treatments
- Known association of the event with the disease under study
- Presence of risk factors in the patient or use of concomitant medications known to increase the occurrence of the event
- Presence of non-treatment-related factors that are known to be associated with the occurrence of the event

5.3.5 Procedures for Recording Adverse Events

Investigators should use correct medical terminology/concepts when recording adverse events on the Adverse Event eCRF. Avoid colloquialisms and abbreviations.

Only one adverse event term should be recorded in the event field on the Adverse Event eCRF.

5.3.5.1 Injection-Site Reactions

Local adverse events that occur within 24 hours after study drug administration and are judged to be related to study drug injection should be captured as an "injection-site reaction" on the Adverse Event eCRF. If possible, avoid ambiguous terms such as "systemic reaction." Associated signs and symptoms (e.g., injection-site erythema or injection-site rash) should be recorded on the dedicated Injection-Site Reaction eCRF. If a patient experiences both a local and systemic reaction to the same administration of study drug, each reaction should be recorded separately on the Adverse Event eCRF. Only for local injection-site reactions should the dedicated Injection-Site Reaction eCRF be used to capture the individual signs/symptoms.

5.3.5.2 Diagnosis versus Signs and Symptoms

A diagnosis (if known) should be recorded on the Adverse Event eCRF rather than individual signs and symptoms (e.g., record only liver failure or hepatitis rather than jaundice, asterixis, and elevated transaminases). However, if a constellation of signs and/or symptoms cannot be medically characterized as a single diagnosis or syndrome at the time of reporting, each individual event should be recorded on the Adverse Event eCRF. If a diagnosis is subsequently established, all previously reported adverse events based on signs and symptoms should be nullified and replaced by one adverse event report based on the single diagnosis, with a starting date that corresponds to the starting date of the first symptom of the eventual diagnosis.

5.3.5.3 Adverse Events That Are Secondary to Other Events

In general, adverse events that are secondary to other events (e.g., cascade events or clinical sequelae) should be identified by their primary cause, with the exception of severe or serious secondary events. A medically significant secondary adverse event

Emicizumab—F. Hoffmann-La Roche Ltd 66/Protocol BO41423, Version 3

that is separated in time from the initiating event should be recorded as an independent event on the Adverse Event eCRF. For example:

- If vomiting results in mild dehydration with no additional treatment in a healthy adult, only vomiting should be reported on the eCRF.
- If vomiting results in severe dehydration, both events should be reported separately on the eCRF.
- If a severe gastrointestinal hemorrhage leads to renal failure, both events should be reported separately on the eCRF.
- If dizziness leads to a fall and consequent fracture, all three events should be reported separately on the eCRF.
- If neutropenia is accompanied by an infection, both events should be reported separately on the eCRF.

All adverse events should be recorded separately on the Adverse Event eCRF if it is unclear as to whether the events are associated.

Bleeds considered as serious adverse events should be reported on the appropriate adverse event eCRF page regardless of whether the bleed is consistent with patients' pre-study disease state (the bleed will remain recorded as well on the BMQ). New, non-serious bleeds consistent with patients' pre-study disease state will not be considered adverse events and will not be recorded on the eCRF but will be captured on the BMQ.

5.3.5.4 Persistent or Recurrent Adverse Events

A persistent adverse event is one that extends continuously, without resolution, between patient evaluation timepoints. Such events should only be recorded once on the Adverse Event eCRF. The initial severity (intensity or grade) of the event will be recorded at the time the event is first reported. If a persistent adverse event becomes more severe, the most extreme severity should also be recorded on the Adverse Event eCRF. If the event becomes serious, it should be reported to the Sponsor immediately (i.e., no more than 24 hours after learning that the event became serious; see Section 5.4.2 for reporting instructions). The Adverse Event eCRF should be updated by changing the event from "non-serious" to "serious," providing the date that the event became serious, and completing all data fields related to serious adverse events.

A recurrent adverse event is one that resolves between patient evaluation timepoints and subsequently recurs. Each recurrence of an adverse event should be recorded as a separate event on the Adverse Event eCRF.

5.3.5.5 Abnormal Laboratory Values

Not every laboratory abnormality qualifies as an adverse event. A laboratory test result must be reported as an adverse event if it meets any of the following criteria:

Is accompanied by clinical symptoms

Emicizumab—F. Hoffmann-La Roche Ltd 67/Protocol BO41423, Version 3

- Results in a change in study treatment (e.g., dosage modification, treatment interruption, or treatment discontinuation)
- Results in a medical intervention (e.g., potassium supplementation for hypokalemia) or a change in concomitant therapy
- Is clinically significant in the investigator's judgment

Note: For oncology trials, certain abnormal values may not qualify as adverse events.

It is the investigator's responsibility to review all laboratory findings. Medical and scientific judgment should be exercised in deciding whether an isolated laboratory abnormality should be classified as an adverse event.

If a clinically significant laboratory abnormality is a sign of a disease or syndrome (e.g., ALP and bilirubin 5×ULN associated with cholestasis), only the diagnosis (i.e., cholestasis) should be recorded on the Adverse Event eCRF.

If a clinically significant laboratory abnormality is not a sign of a disease or syndrome, the abnormality itself should be recorded on the Adverse Event eCRF, along with a descriptor indicating whether the test result is above or below the normal range (e.g., "elevated potassium," as opposed to "abnormal potassium"). If the laboratory abnormality can be characterized by a precise clinical term per standard definitions, the clinical term should be recorded as the adverse event. For example, an elevated serum potassium level of 7.0 mEg/L should be recorded as "hyperkalemia."

Observations of the same clinically significant laboratory abnormality from visit to visit should only be recorded once on the Adverse Event eCRF (see Section 5.3.5.4 for details on recording persistent adverse events).

5.3.5.6 Abnormal Vital Sign Values

Not every vital sign abnormality qualifies as an adverse event. A vital sign result must be reported as an adverse event if it meets any of the following criteria:

- Is accompanied by clinical symptoms
- Results in a change in study treatment (e.g., dosage modification, treatment interruption, or treatment discontinuation)
- Results in a medical intervention or a change in concomitant therapy
- Is clinically significant in the investigator's judgment

It is the investigator's responsibility to review all vital sign findings. Medical and scientific judgment should be exercised in deciding whether an isolated vital sign abnormality should be classified as an adverse event.

Emicizumab—F. Hoffmann-La Roche Ltd 68/Protocol BO41423, Version 3

If a clinically significant vital sign abnormality is a sign of a disease or syndrome (e.g., high blood pressure), only the diagnosis (i.e., hypertension) should be recorded on the Adverse Event eCRF.

Observations of the same clinically significant vital sign abnormality from visit to visit should only be recorded once on the Adverse Event eCRF (see Section 5.3.5.4 for details on recording persistent adverse events).

5.3.5.7 Abnormal Liver Function Tests

The finding of an elevated ALT or AST ($>3 \times ULN$) in combination with either an elevated total bilirubin ($>2 \times ULN$) or clinical jaundice in the absence of cholestasis or other causes of hyperbilirubinemia is considered to be an indicator of severe liver injury (as defined by Hy's Law). Therefore, investigators must report as an adverse event the occurrence of either of the following:

- Treatment-emergent ALT or AST > 3 × ULN in combination with total bilirubin > 2 × ULN
- Treatment-emergent ALT or AST > 3 × ULN in combination with clinical jaundice

The most appropriate diagnosis or (if a diagnosis cannot be established) the abnormal laboratory values should be recorded on the Adverse Event eCRF (see Section 5.3.5.2) and reported to the Sponsor immediately (i.e., no more than 24 hours after learning of the event), either as a serious adverse event or an adverse event of special interest (see Section 5.4.2).

5.3.5.8 Deaths

All deaths that occur during the protocol-specified adverse event reporting period (see Section 5.3.1), regardless of relationship to study drug, must be recorded on the Adverse Event eCRF and immediately reported to the Sponsor (see Section 5.4.2). This includes death attributed to progression of hemophilia.

Death should be considered an outcome and not a distinct event. The event or condition that caused or contributed to the fatal outcome should be recorded as the single medical concept on the Adverse Event eCRF. Generally, only one such event should be reported. If the cause of death is unknown and cannot be ascertained at the time of reporting, "unexplained death" should be recorded on the Adverse Event eCRF. If the cause of death later becomes available (e.g., after autopsy), "unexplained death" should be replaced by the established cause of death. The term "sudden death" should not be used unless combined with the presumed cause of death (e.g., "sudden cardiac death").

If the death is attributed solely to progression of hemophilia, "hemophilia progression" should be recorded on the Adverse Event eCRF.

Deaths that occur after the adverse event reporting period should be reported as described in Section 5.6.

Emicizumab—F. Hoffmann-La Roche Ltd 69/Protocol BO41423, Version 3

5.3.5.9 Preexisting Medical Conditions

A preexisting medical condition is one that is present at the screening visit for this study. Such conditions should be recorded on the General Medical History and Baseline Conditions eCRF.

A preexisting medical condition should be recorded as an adverse event only if the frequency, severity, or character of the condition worsens during the study. When recording such events on the Adverse Event eCRF, it is important to convey the concept that the preexisting condition has changed by including applicable descriptors (e.g., "more frequent headaches").

5.3.5.10 Lack of Efficacy or Worsening of Hemophilia

Medical occurrences or symptoms of deterioration that are anticipated as part of hemophilia should be recorded as an adverse event if judged by the investigator to have unexpectedly worsened in terms of severity (e.g., increased number of doses of FVIII to stop bleeds with emicizumab, in the absence of neutralizing anti-emicizumab antibodies, compared with before study entry), frequency of bleeds, or nature of hemophilia at any time during the study. When recording an unanticipated worsening of hemophilia on the Adverse Event eCRF, it is important to convey that the underlying condition has changed by including applicable descriptors (e.g., "increased clinical severity of hemophilia"). A clinically significant bleed (i.e., Intracranial, retroperitoneal) does not by itself constitute loss of efficacy, unless it is associated with features indicating worsening of the underlying hemophilia phenotype.

Events that are clearly consistent with the anticipated pattern of the underlying disease and do not indicate an unexpected worsening in severity or frequency should not be recorded as adverse events. These data will be reflected in efficacy assessment data only.

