5.2.1 Adverse Events

According to the ICH guideline for Good Clinical Practice, an adverse event is any untoward medical occurrence in a clinical investigation subject administered a pharmaceutical product, regardless of causal attribution. An adverse event can therefore be any of the following:

 Any unfavorable and unintended sign (including an abnormal laboratory finding), symptom, or disease temporally associated with the use of a medicinal product, whether or not considered related to the medicinal product

Emicizumab—F. Hoffmann-La Roche Ltd 62/Protocol BO41423, Version 3

- Any new disease or exacerbation of an existing disease (a worsening in the character, frequency, or severity of a known condition) (see Sections 5.3.5.9 and 5.3.5.10 for more information)
- Recurrence of an intermittent medical condition (e.g., headache) not present at baseline
- Any deterioration in a laboratory value or other clinical test (e.g., ECG, X-ray) that is
 associated with symptoms or leads to a change in study treatment or concomitant
 treatment or discontinuation from study drug
- Adverse events that are related to a protocol-mandated intervention, including those that occur prior to assignment of study treatment (e.g., screening invasive procedures such as biopsies)

5.2.2 Serious Adverse Events (Immediately Reportable to the Sponsor)

A serious adverse event is any adverse event that meets any of the following criteria:

- Is fatal (i.e., the adverse event actually causes or leads to death)
- Is life threatening (i.e., the adverse event, in the view of the investigator, places the patient at immediate risk of death)

This does not include any adverse event that, had it occurred in a more severe form or was allowed to continue, might have caused death.

- Requires or prolongs inpatient hospitalization (see Section 5.3.5.11)
- Results in persistent or significant disability/incapacity (i.e., the adverse event results in substantial disruption of the patient's ability to conduct normal life functions)
- Is a congenital anomaly/birth defect in a neonate/infant born to a mother exposed to study drug
- Is a significant medical event in the investigator's judgment (e.g., may jeopardize the
 patient or may require medical/surgical intervention to prevent one of the outcomes
 listed above)

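### Sections 5.3.5.3 and 5.3.5.10 of the protocol give opposite reporting instructions for a non-fatal serious bleed that fits the patient's usual disease pattern, so SAE counts and 24-hour reporting can be understated

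*Protocol*

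**What the plan says.** Protocol Section 5.3.5.3 ends with a rule written specifically for bleeds: "Bleeds considered as serious adverse events should be reported on the appropriate adverse event eCRF page regardless of whether the bleed is consistent with" the patient's disease before the study. Its counterpart covers only new, non-serious bleeds of the familiar kind, which "will not be considered adverse events and will not be recorded on the eCRF but will be captured on the BMQ".

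Protocol Section 5.3.5.10 has a broader rule. Events that clearly match the anticipated disease pattern and show no "unexpected worsening in severity or frequency should not be recorded as adverse events. These data will be reflected in efficacy assessment data only". The paragraph is not limited to non-serious events and does not refer to 5.3.5.3. The preceding paragraph adds: "A clinically significant bleed (i.e., Intracranial, retroperitoneal) does not by itself constitute loss of efficacy", unless there are signs that the underlying phenotype is worsening.

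The adverse event definition in Section 5.2.1, in its item on new or exacerbated disease, tells the reader to "see Sections 5.3.5.9 and 5.3.5.10 for more information". It does not mention 5.3.5.3.

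Section 5.2.2 builds the SAE definition on the AE definition: "A serious adverse event is any adverse event that meets any of the following criteria". Sections 5.2.2 and 5.4 attach the 24-hour reporting duty to SAEs, and SAP Section 3.7.2 plans a separate SAE summary.

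**The concern.** Take a patient admitted to hospital, without prior planning, for a joint bleed of the kind the patient had before the study. Section 5.3.5.3 makes this a reportable SAE. Section 5.3.5.10, if the investigator judges that nothing has unexpectedly worsened, says that it is not an adverse event at all.

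SAE incidence is a core safety output of a single-arm, descriptive study, and there is no control arm in which the same under-recording would occur. Serious bleeds on prophylaxis are also events that a reader of the safety tables will look for. If sites resolve the conflict differently, the SAE percentage partly reflects reporting habit. Prompt notice to the sponsor, and the sponsor's evaluation of SAEs under Section 5.7, depend on the same choice.

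**Working it through.** The plan states no figure on this point, so the check is a comparison of rules, followed by one scale calculation.

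**Step 1: the event that meets both rules.** It is a bleed that is (a) non-fatal, (b) meets a seriousness criterion in Section 5.2.2, and (c) is judged clearly consistent with the patient's usual pattern.

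| Question | Section 5.3.5.3 | Section 5.3.5.10 |
|---|---|---|
| Does the rule depend on seriousness? | Yes, it decides the route | No |
| Does consistency with prior disease matter? | Not for serious bleeds | Yes, it excludes the event, absent unexpected worsening |
| Recorded on the AE eCRF? | Yes | No |
| Where is it kept? | AE eCRF and BMQ | Efficacy data only |
| Refers to the other section? | No | No |

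The two instructions are opposite for this event, and no precedence is stated.

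**Step 2: does seriousness count as worsening under 5.3.5.10?** Not by its wording. The test there is unexpected worsening in severity, frequency or nature. Section 5.2.2 says that severity and seriousness are to be judged independently. The sentence on intracranial and retroperitoneal bleeds confirms that a grave bleed alone does not amount to loss of efficacy under that section.

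**Step 3: does the SAE definition rescue the event?** No. An SAE must first be an AE. An investigator who applies 5.3.5.10 first concludes that there is no AE, and so never reaches the category that 5.3.5.3 addresses. The hospitalization rule in Section 5.3.5.11 also starts from an adverse event, so it does not settle the matter alone.

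**Step 4: is the bleed recovered elsewhere?** No. Section 4.5.7 lists the BMQ as a patient-reported outcome instrument. Section 5.3.5.13 says that the sponsor derives no adverse event reports from such data and runs no safety analyses on them. The SAP has no rule for serious bleeds.

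**Step 5: scale.** The planned sample size is about 70 (Protocol Section 6.1), and SAP Section 3.7.2 bases percentages on the number of patients overall. For one patient whose only SAE is such a bleed:

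change in SAE incidence = 1/70 = 0.0143, or about 1.4 percentage points.

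A patient who has another SAE as well does not change the percentage. Relative to 5.3.5.3, following 5.3.5.10 can only lower the count.

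**The case against.** The strongest reply is that the protocol already answers the case. Section 5.3.5.3 deals with bleeds by name and says explicitly that consistency with prior disease is irrelevant, whereas 5.3.5.10 speaks of events in general. The specific rule is the natural one to prevail, and Section 5.3 binds sites to all of its instructions. Section 5.3.5.11 points the same way, since an unplanned admission for a bleed is not among its exceptions. This reading is plausible, and a careful investigator may well adopt it. It does not remove a written rule that gives the opposite result when followed. The specific rule also stands at the end of a section about events secondary to other events, while the AE definition directs the reader to 5.3.5.10.

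Other parts of the reply succeed in limiting the point. A reader might infer that a site following 5.3.5.10 would report no serious bleeds at all. The section does not say that: it excludes only events clearly consistent with the anticipated pattern, and a first hospitalized or life-threatening bleed can readily be judged an unexpected worsening, which the section requires to be recorded.

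A reader might also infer a second barrier in Section 5.3.5.9, which admits a preexisting condition as an adverse event only if "the frequency, severity, or character of the condition worsens during the study". That is weak, because the section concerns conditions present at screening, and a bleed on study is a new event.

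Finally, a reader might infer from Section 5.3.5.8 that fatal bleeds could be hidden under a hemophilia-progression term. The documents do not support this. That term is reserved for the case "If the death is attributed solely to progression of hemophilia", and the same section requires every death in the reporting period to be reported, with the causal event as the recorded term.

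**Conclusion.** The contradiction stands, within narrow bounds. It concerns non-fatal bleeds that meet a seriousness criterion and are judged to fit the patient's usual pattern. For these, SAE incidence and 24-hour reporting can be understated, depending on which section a site applies.

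The size per affected patient is about 1.4 percentage points, assuming about 70 treated patients and no other SAE in that patient. It is tempting to multiply an assumed bleed rate by an assumed serious fraction to obtain a total, but the documents do not support this. The median annualized bleed rate of 3 in Protocol Section 1.1 belongs to a registry group, not to patients in this trial, and no fraction of serious bleeds is given anywhere. The total effect cannot be computed from the documents.

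The primary and secondary bleed-rate endpoints are not affected, because the bleed stays on the BMQ under either section. This is an internal inconsistency that should be corrected; it does not undermine the efficacy analysis.

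**What to change.** Reconcile the two sections in the next protocol amendment, using the rule that 5.3.5.3 already states:

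- In the last paragraph of 5.3.5.10, limit the exclusion to non-serious events.
- In the same paragraph, add that a bleed meeting a seriousness criterion is reported as an SAE under 5.3.5.3 and also remains on the BMQ.
- In Section 5.2.1, add 5.3.5.3 to the existing cross-reference.

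No change to 5.3.5.8 or 5.3.5.9 is needed. The cost is a few lines of text. The one downside for the sponsor is that the SAE percentage may look slightly less favourable.
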